9.4.5.2 Change from Baseline

Change from baseline will be calculated as

Change of Baseline = Assessment Value – Baseline Assessment Value.

9.4.5.3 Percent Change from Baseline

Percent change from baseline will be calculated as

Percent Change of Baseline = [(Assessment Value – Baseline Assessment Value)/(Baseline Assessment Value)]*100

and rounded to 1 more decimal place than observed in the raw data.

9.4.6 United Kingdom Model for End-Stage Liver Disease

The UK-MELD is calculated as (5.395 x lnINR) + (1.485 x ln serum creatinine) + (3.13 x ln serum bilirubin) - (81.565 x ln serum sodium) + 435.

9.4.7 Adverse Events

The analysis of Adverse Events is described in detail in Section 7.2.2.

9.4.7.1 Treatment-emergent Adverse Events (TEAEs)

Treatment-emergent AEs (TEAEs) are events with start dates and start times on or after the date and time of the first study drug dose (SBC-102). All other AEs are considered Pre-Treatment Adverse Events (PTAEs).

Subject percentages are based on the total number of treated subjects.

The relationship between an AE and the study drug will be classified as: not related; unlikely related; possibly related; or related. AEs assessed as "possibly related" or "related" are further categorized as "Related AEs". AEs assessed as "not related" or "not related" are further categorized as "Unrelated AEs".

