7.1. Adverse Events and Laboratory Abnormalities

7.1.1. Clinical Adverse Events

An **Adverse Event** is any untoward medical occurrence in a subject, which does not necessarily have to have a causal relationship with the administration of a study drug. An AE can therefore be any unfavorable and unintended sign, symptom, or disease temporally associated with the use of the study drug, whether or not considered related to the medicinal product. Pre-existing conditions that worsen in severity during the course of the study are to be reported as AEs. All AEs occurring during the clinical study and related to study conduct, will be reported on the AE page of the eCRF, as described in [Section 7.3](#). The Investigator will assess the severity, causality (relationship to study drug), and seriousness of each AE.

Severity: The Investigator will assess the severity of all AEs/SAEs as mild, moderate, or severe, based on the following definitions (developed from Clinical Data Interchange Standards Consortium Study Data Tabulation Model standard terminology v3.1.1).

- **Mild**: A type of AE that is usually transient and may require only minimal treatment or therapeutic intervention. The event does not generally interfere with usual activities of daily living.
- **Moderate**: A type of AE that is usually alleviated with additional specific therapeutic intervention. The event interferes with usual activities of daily living, causing discomfort, but poses no significant or permanent risk of harm to the research participant.
- **Severe**: A type of AE that interrupts usual activities of daily living, significantly affects clinical status, or may require intensive therapeutic intervention.

Causality: AEs will be assessed as not related, unlikely related, possibly related, or related to study drug. [Table 5](#) provides general guidance on the assessment of causality. For data reporting purposes, AEs assessed as not related or unlikely related will be reported as unrelated to study drug, and AEs assessed as possibly related or related will be reported as related to study drug. Assessment of causality will be based on the Investigator's medical judgment and the observed symptoms associated with the event.

Table 5 Assessment of Causality

| Relationship to Study Drug | Criteria for Judgment |
|----------------------------|---|

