7.2. Handling of Safety Parameters

7.2.1. Serious Adverse Events and Moderate or Severe Infusion-Associated Reactions (Immediately Reportable to Sponsor)

All SAEs and IARs (serious and nonserious), must be reported to the Sponsor or designee immediately and no later than 24 hours after the Investigator's first knowledge of the event.

Adverse Event Reporting Period

The study period during which AEs must be reported is defined as the period from signature of the informed consent to the end of the study treatment follow-up. Adverse events occurring after signing the informed consent but prior to the first dose of study medication will only be recorded if assessed as related to protocol procedures or requirements. For this study, the study treatment follow-up is defined as a minimum of 4 weeks following the last administration of study treatment. If a subject experiences an SAE that is considered to be related to study treatment at any time after the study, it must be reported to the Sponsor.

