7.3. Recording of Adverse Events

At each scheduled contact with the subject (or the subject's parent or legal guardian) the Investigator must seek information on AEs by specific questioning and, as appropriate, by examination. Information on all AEs must be recorded in the source document, and in the eCRF. All clearly related signs, symptoms, and abnormal diagnostic procedures results should be recorded under one diagnosis.

AEs will be recorded from the time of signing of the informed consent until completion of the last scheduled visit, i.e., the follow-up visit. Adverse events occurring after signing the informed consent but prior to the first dose of study medication will only be recorded if assessed as related to protocol procedures or requirements.

Any AEs remaining unresolved after completion of the last scheduled visit should be recorded as ongoing. Ongoing AEs/SAEs should continue to be followed up for the period specified in [Section 7.2.2](#) but without further recording in the eCRF. However, follow-up information on SAEs must be reported to the Sponsor or designee as described in Section 7.4. Any SAE that occurs after the study period and is considered to be related to the study treatment or study participation should be recorded and reported immediately.

Any AE that occurs within 24 hours of the infusion will be recorded by time and date. Adverse events occurring 24 hours after the infusion will be recorded by date only. The date and time, or the date when the AE started and stopped, as well as the intensity, seriousness, action taken with regard to the study treatment, causality assessment and outcome of the event will be recorded for each AE.

7.4. Reporting of Serious Adverse Events, Infusion-Associated Reactions and Unanticipated Problems

Investigators and the Sponsor must conform to the AE reporting timelines, formats and requirements of the various entities to which they are responsible (§13 GCP-V; Detailed guidance on the collection, verification and presentation of adverse event/reaction reports arising from clinical trials on medicinal products for human use ['CT-3']; US Code of Federal Regulations Title 21, §312.32, Investigational New Drug [IND] safety reporting).

The Sponsor or designee will report all reportable events to all regulatory authorities, IECs or IRBs, and Investigators as required by local regulations.

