7.2.2. Adverse Events and Infusion-Associated Reactions

Adverse Events (AE) will be coded by primary system organ class (SOC) and preferred term (PT) using the Medical Dictionary for Regulatory Activities (MedDRA) (version 15.1 or higher). AEs will be determined as occurring from the signing of informed consent and prior to the initiation of SBC-102 (pre-treatment AEs), or as on/after first dose of SBC-102 (treatment-emergent) as described in Section 9.4.7. Pre-Treatment Adverse Events (PTAEs) will be presented in listings only, and Treatment-Emergent Adverse Events (TEAEs) will be presented in summary tables and listings.

Study displays for TEAEs are described below.

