9.4.7.2 Missing AE Dates

If the start date of an AE is partially or completely missing and the end (stop) date and time of the AE does not indicate that it occurred prior to first dose, then the determination of treatment-emergent status will be based on the following:

- If the start year is after the year of the first study drug dose, then the AE is treatment-emergent; else,
- If the start year is the same as the year of the first study drug dose and
 - the start month is missing, then the AE is treatment emergent; else if
 - the start month is present and is the same or after the month of the first study drug dose, then the AE is treatment-emergent; else.
- If the start date is completely missing, then the AE is treatment-emergent.

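### The SAP's treatment-emergent rule demands a start time and has no worsening clause, so read literally it can move some post-dose adverse events out of the safety tables

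*SAP*

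**What the plan says.** - SAP 9.4.7.1 gives the definition: "Treatment-emergent AEs (TEAEs) are events with start dates and start times on or after the date and time of the first study drug dose (SBC-102". The remainder is assigned outright: "All other AEs are considered Pre-Treatment Adverse Events (PTAEs". There is no clause for an event that worsens after dosing.
- SAP 7.2.2 sets the consequence: "Pre-Treatment Adverse Events (PTAEs) will be presented in listings only". The summary tables are built from treatment-emergent AEs (TEAEs), and SAP 5.1.1 makes their incidence and severity part of the primary safety assessment.
- SAP 9.4.7.2 is the only rule for incomplete onset data. It opens "If the start date of an AE is partially or completely missing" and does not mention a missing start time. For an onset in the same year as first dose it says that if "the start month is present and is the same or after the month of the first study drug dose, then the AE is treatment-emergent". A wholly missing start date is also treatment-emergent. All of this applies unless the stop date places the event before first dose.
- Protocol 7.3 on timing: "Any AE that occurs within 24 hours of the infusion will be recorded by time and date". Later AEs are recorded by date alone.
- Protocol 7.1.1: "Pre-existing conditions that worsen in severity during the course of the study are to be reported as AEs". It does not say which start date such an AE carries.
- Protocol 7.2.1 says that AEs arising after consent but "prior to the first dose of study medication will only be recorded if assessed as related to protocol procedures or requirements". Protocol 7.3 repeats this.

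**The concern.** The rule in SAP 9.4.7.1 is complete as written: an AE either meets the date-and-time test or becomes a pre-treatment AE (PTAE). Three kinds of AE can fail the test although they arise or get worse on treatment.

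1. An AE on the first-dose day whose start time was not collected.
2. An AE with onset between consent and first dose, or a pre-existing condition entered under the date it first appeared, that worsens after dosing within one record.
3. On the strictest reading, every later AE recorded by date alone, because it has no time to compare.

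An AE that fails leaves the incidence, severity and relationship tables and survives only in a listing. In a small uncontrolled study whose primary objective is safety, those tables are the main result. The first case also sits badly with SAP 9.4.7.2, which resolves doubt the other way.

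**Working it through.** The plan states no figure on this point, so there is none to reproduce. The check runs five example AEs through the SAP rules and then works out what one reclassified subject is worth.

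**Step 1: three readings of SAP 9.4.7.1 and 9.4.7.2**

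- A: both date and time must be present and at or after first dose.
- B: the date decides; time matters only on the first-dose day.
- C: as B, but a missing time on the first-dose day counts as a partly missing start date under 9.4.7.2.

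| Example AE | A | B | C |
|---|---|---|---|
| First-dose day, time recorded after dosing | TEAE | TEAE | TEAE |
| First-dose day, time missing | PTAE | PTAE | TEAE |
| Three days after dosing, date only | PTAE | TEAE | TEAE |
| Worsening entered as its own AE, dated at the worsening, date only | PTAE | TEAE | TEAE |
| Onset before dosing, one record, worsens later | PTAE | PTAE | PTAE |

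The last row is a PTAE on every reading. The untimed first-dose-day AE is a PTAE on two of the three. Reading C has to treat a complete calendar date as partly missing. That is a strain, because the opening sentence of 9.4.7.2 names date and time together for the stop of the AE but only date for its start.

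Reading A would exclude AEs recorded exactly as protocol 7.3 instructs, so it is unlikely to be what anyone would program. SAP 9.4.4, on study day, uses clock time only for measurements on the day of first infusion, which favours B as the intended approach. It gives no default for a missing time either.

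**Step 2: direction of the defaults, side by side**

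- Onset known only to the month of first dose: treatment-emergent (9.4.7.2).
- Onset known to the day of first dose, time missing: pre-treatment (9.4.7.1, readings A and B).

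The better-documented event gets the less conservative class. The protocol's recording rule points the same way: if it is followed, a pre-dose AE is on file only when tied to a study procedure or requirement. Any other AE recorded on that day must therefore be post-dose.

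**Step 3: what one subject is worth**

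The shift in a table row is 100 × k / N, where k is the number of subjects wrongly moved out. Protocol 8.2 expects about 30 treated subjects; SAP 9.3 expects no more than 20.

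- k = 1: 100 × 1/30 = 3.3 points; 100 × 1/20 = 5.0 points.
- k = 3 (assumed, for scale only): 100 × 3/30 = 10.0 points; 100 × 3/20 = 15.0 points.

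The actual k cannot be derived from the documents. SAP 7.2.2.2 counts a subject once per term, so a subject leaves a row only if no other event of that term is treatment-emergent.

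**The case against.** The strongest answer is that the protocol already closes most of the gap.

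- A post-dose AE on the first-dose day falls within 24 hours of an infusion, so its time is mandatory. The problem needs a required field to stay blank through the query resolution that SAP 7.14 plans before the first lock.
- SAP 7.2.2 describes pre-treatment AEs as those before the start of study drug, and an untimed event is not shown to be one.
- A worsening of a pre-existing condition is reportable as an AE and is treatment-emergent if dated at the worsening. Clinically significant laboratory changes are handled the same way (SAP 5.1.1.4).
- An infusion-associated reaction occurs during or after an infusion by definition (protocol 7.1.3), and serious AEs and these reactions have their own forms and summaries. Nothing disappears from the listings.

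Most of this stands as a limit on frequency. It does not supply the missing rule. Dates are mandatory too, yet the SAP still provides for missing ones. SAP 7.2.2 refers to 9.4.7 for the classification, so the literal test governs. Neither document says which start date a worsened condition carries, and a pre-dose AE that worsens inside one record is a PTAE on any reading.

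**Conclusion.** The point holds as a defect in a stated rule, with a probable effect of few events and a risk towards fewer TEAEs. Each subject affected is worth 3.3 points in a row at N = 30 or 5.0 at N = 20, provided the subject has no other treatment-emergent event of the same term.

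A reader might infer three stronger things, none of which the documents support.

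- That every AE starting before and worsening after dosing is lost. A worsening entered as its own AE with its own date is treatment-emergent on readings B and C; the outcome turns on a start date the documents leave open.
- That the primary safety tables do undercount. No affected count can be derived, and the untimed first-dose-day case requires a lapse in data collection.
- That the loss falls mainly on progressing liver or gut disease. AEs recorded before dosing are limited to those tied to study procedures or requirements, so the single-record case mainly concerns events such as complications of screening procedures. Underlying disease is caught only if its worsening is entered under the date the condition first appeared, which is an assumption.

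The strictest reading, which would remove date-only AEs, is a reason to tidy the wording rather than a likely outcome.

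**What to change.** In SAP 9.4.7.1, define a TEAE as an AE that starts, or worsens in severity, on or after the first dose. State that the date of worsening serves as the start date of a worsened event, and that time is compared only when the start date is the first-dose date.

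In SAP 9.4.7.2, add that an AE starting on the first-dose date with a missing time is treatment-emergent unless the record shows onset before the infusion.

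The cost is a few lines of SAP text and matching programming, with no new assessments. Where a worsening was kept inside one record, its date must be in that record or be queried from the site. TEAE counts may rise slightly, and a few events that truly preceded the first infusion may be counted. That is the same conservative direction the SAP already takes for missing dates.

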9.4.7.2 Missing AE Dates

If the start date of an AE is partially or completely missing and the end (stop) date and time of the AE does not indicate that it occurred prior to first dose, then the determination of treatment-emergent status will be based on the following:

- If the start year is after the year of the first study drug dose, then the AE is treatment-emergent; else,
- If the start year is the same as the year of the first study drug dose and
 - the start month is missing, then the AE is treatment emergent; else if
 - the start month is present and is the same or after the month of the first study drug dose, then the AE is treatment-emergent; else.
- If the start date is completely missing, then the AE is treatment-emergent.

9.4.7.3 AE Duration (Days)

AE Duration (days) = Date of stop of AE – Date of start of AE + 1;

Duration will be set to 'missing' if dates are incomplete.

9.4.8 Calculation of Multiples of Normal for Liver and Spleen Volume

Multiples of Normal (MN) are derived by determining the expected "normal" weight of a specific organ based on body weight.

- Liver: 2.5% of body weight in kg gives the expected "normal" liver weight in liters;
- Spleen: 0.2% of body weight in kg gives the expected "normal" spleen volume in liters

For example: a 50 kg subject would have an expected "normal" liver volume of 1.25 liters (0.025*50=1.25) and an expected "normal" spleen volume of 0.10 liters (0.002*50=0.1). The patient's observed organ volume is then divided by the expected "normal" volume. Values of MN >1.0 indicate an organ volume which is larger than the expected normal volume.

9.4.9 Health-Related Quality of Life Questionnaires

9.4.9.1 The Functional Assessment of Chronic Illness Therapy (FACIT) Fatigue scale

The FACIT-Fatigue instrument consists of 13 items, with each item rated on a 4-point ordinal scale ranging from 0 (Not at all) to 4 (Very Much).

		Not at	A little	Somewhat	Quite a	Very
		all	bit	Joinewhat	bit	Much
4	I feel fatigue	0	1	2	3	4
-	•			2	3	
2	I feel weak all over	0	1		3	4
3	I feel listless ("washed out")	0	1	2	3	4
4	I feel tired	0	1	2	3	4
5	I have trouble starting things because I	0	1	2	3	4
	am tired					
6	I have trouble finishing things because I	0	1	2	3	4
	am tired					
7	I have energy	0	1	2	3	4
8	I am able to do my usual activities	0	1	2	3	4
9	I need to sleep during the day	0	1	2	3	4
10	I am too tired to eat	0	1	2	3	4
11	I need help doing my usual activities	0	1	2	3	4
12	I am frustrated by being too tired to do	0	1	2	3	4
	things I want to do					
13	I have to limit my social activity	0	1	2	3	4
	because I am tired					

Scoring of FACIT-Fatigue: The total score ranges from 0-52. Higher scores suggest better quality of life for the subject. All items, except Items #7 and #8, are reversed scored.

	Reverse Item?		Item Response	Item Score
1	4	-		=
2	4	-		=
3	4	-		=
4	4	-		=
5	4	-		=
6	4	-		=
7	0	+		=
8	0	+		=
9	4	-		=
10	4	-		=
11	4	-		=
12	4	-		=
13	4	-		=

Total Score: (sum of Item Scores) * 13 and divide by the number of items answered.

Missing Data: The total FACIT-Fatigue Scale can be calculated as long as more than 50% of the items were answered (e.g. a minimum of 7 of 13 items).

9.4.9.2 The Chronic Liver Disease Questionnaire (CLDQ)

CLDQ is a 29-item instrument to measure quality of life in 6 domains: abdominal symptoms; fatigue; systemic symptoms; activity; emotional function; and worry. Each item is rated on a 7-point ordinal scale ranging from 1 (All of the time) to 7 (none of the time).

Domains of the CLDQ:

Abdominal Symptoms (AB):	Items 1, 5, 17
Fatigue (FA):	Items 2, 4, 8, 11, 13
Systemic Symptoms (SY):	Items 3, 6, 21, 23, 27
Activity (AC):	Items 7, 9, 14
Emotional Function (EM):	Items 10, 12, 15, 16, 19, 20, 24, 26
Worry (WO):	Items 18, 22, 25, 28, 29;

Scoring of CLDQ:

Single domains and overall score range from 1-7. Higher scores implicate a better quality of life.

Single domain = (Sum individual item scores) x (number of scheduled items per domain) and divide by number of items answered.

Total score = (Sum single domains) divide by 6.

Total score can only be calculated if each single domain score is available.

Missing data:

Single domain scores can be calculated as long as more than 50% of the items were answered (e.g. a minimum of 2 of 3 items, 3 of 5 items, 4 of 8 items).

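### The CLDQ formula in SAP 9.4.9.2 does not produce the stated 1-7 scores: domains run up to 56, the total runs 4.83 to 33.83, and the total is weighted by domain length

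*SAP*

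**What the plan says.** SAP section 9.4.9.2 describes the instrument and its scoring. "CLDQ is a 29-item instrument to measure quality of life in 6 domains", and "Each item is rated on a 7-point ordinal scale ranging from 1 (All of the time) to 7 (none of the time". The items are allotted to domains by number; Fatigue, for example, has "Items 2, 4, 8, 11, 13" and Emotional Function has "Items 10, 12, 15, 16, 19, 20, 24, 26".

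For the scores it states: "Single domains and overall score range from 1-7". The domain rule is: "Single domain = (Sum individual item scores) x (number of scheduled items per domain) and divide by number of items answered". The total is the sum of the six domain scores divided by 6, and exists only if all six are available. A domain may be scored if "more than 50% of the items were answered (e.g. a minimum of 2 of 3 items, 3 of 5 items, 4 of 8 items".

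SAP section 7.8 plans to summarise changes in overall and subscale scores for each HRQOL instrument, with 95% confidence intervals. Nothing elsewhere in the SAP or protocol rescales the CLDQ domains.

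**The concern.** The stated range and the formula sit in the same section and cannot both be met. With items scored 1 to 7, a score that runs 1 to 7 must be an average. The formula instead multiplies back up by the number of items, which gives a sum.

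This is more than a change of units. A single common multiplier could be undone by any reader. Here the multiplier is the domain's own item count (3, 5 or 8), so domains are on three different scales, and adding them and dividing by 6 weights each by its length. Someone told that the scale is 1-7 would read absolute changes as several times too large, and the total would no longer be the equal-weight average of six domains that dividing by 6 suggests.

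The missing-data rule has a separate fault: the wording demands more than half the items, but the example for the 8-item domain allows exactly half. Because the total needs all six domains, that one case can decide whether a subject has a total score.

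**Working it through.** **Inputs, all from SAP 9.4.9.2.** Items are scored 1 to 7. Counting the listed items gives *k* = 3 (Abdominal Symptoms), 5 (Fatigue), 5 (Systemic Symptoms), 3 (Activity), 8 (Emotional Function) and 5 (Worry). 3 + 5 + 5 + 3 + 8 + 5 = 29, which agrees with the stated length of the instrument.

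**Can the plan's 1-7 be reproduced?** Let *S* be the sum of the answered items, *a* the number answered and *m* = *S*/*a* the mean item score, which lies between 1 and 7.

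- As written: domain = *S* × *k* / *a* = *k* × *m*, so the range is *k* to 7*k*. The stated range is not reproduced.
- Item mean: domain = *S* / *a* = *m*, range 1 to 7; total = sum of six means / 6, range 1 to 7. The stated range is reproduced for both.
- Sum of all items / 29: the total runs 1 to 7, but this is not the written formula and leaves the domains unchanged.

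Of these, only the item mean gives 1-7 for domains and total together.

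**Size of the discrepancy.**

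| Domain | *k* | Range as written | Change in total per 1-point gain on all its items, as written (*k*/6) | Weight in total as written (*k*/29) |
|---|---|---|---|---|
| Abdominal Symptoms | 3 | 3-21 | 0.50 | 10.3% |
| Activity | 3 | 3-21 | 0.50 | 10.3% |
| Fatigue | 5 | 5-35 | 0.83 | 17.2% |
| Systemic Symptoms | 5 | 5-35 | 0.83 | 17.2% |
| Worry | 5 | 5-35 | 0.83 | 17.2% |
| Emotional Function | 8 | 8-56 | 1.33 | 27.6% |

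With item means, each domain moves the total by 1/6 = 0.167 and has weight 16.7%.

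Total as written: minimum 29/6 = 4.83, maximum 7 × 29/6 = 203/6 = 33.83. A 1-point gain on every item moves it by 29/6 = 4.83; with item means the gain is 1.0.

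**Is this only a missing-data effect?** No. With all items answered *a* = *k*, and the domain is simply the item sum. With partial answers the formula prorates to the same range: 2 of 3 items at 1 gives 2 × 3/2 = 3; 5 of 8 items at 7 gives 35 × 8/5 = 56.

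**Does the weighting change results?** Take all items at 5, then let one domain fall to 3.

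- As written, the total starts at 145/6 = 24.17. If Emotional Function falls, it becomes (145 − 16)/6 = 21.50, a drop of 11.0%. If Abdominal Symptoms falls, it becomes (145 − 6)/6 = 23.17, a drop of 4.1%.
- With item means, the total goes from 5 to 28/6 = 4.67 in either case, a drop of 6.7%.

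**Comparison with the neighbouring instruments.** The CLDQ rule has the same form as the FACIT-Fatigue rule in 9.4.9.1 (sum × 13 / items answered). There it is right: 13 items scored 0-4 give the stated 0-52. The PedsQL rule in 9.4.9.3 divides by the number of responses, which is the form that the CLDQ's stated range requires.

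**Missing-data rule.** 2/3 = 67% and 3/5 = 60% both exceed 50%. 4/8 = 50% does not. Read strictly, the minimum for the 8-item domain is 5.

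**The case against.** The arithmetic is not in dispute; the case on the other side is about consequence.

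First, the primary objective is safety, HRQOL is an exploratory objective, and all analyses are descriptive. The CLDQ is completed only by subjects aged 17 or older at consent, a subset of about 30 subjects (protocol 8.2) or at most 20 (SAP 9.3). No sample size, dosing or safety decision uses it. This stands and limits the effect on the trial's conclusions.

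Second, not every output is affected. Within one domain *k* is constant, so the direction of change and the percent change are the same under either formula. This also stands. It does not extend to absolute domain values and changes, or to the total and its absolute and percent change.

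Third, some scores would still fall numerically between 1 and 7: low values in the 3- and 5-item domains, and the lowest totals. Only Emotional Function, with a minimum of 8, never could. So the mismatch is between ranges, not a breach by every single value. Likewise Emotional Function has the largest weight but does not dominate: the other five domains carry 21/29 = 72.4%.

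Fourth, a programmer would probably notice an 8 or a 35 on a scale described as 1-7, and listed data allow later re-derivation. That lowers the risk but leaves the programmer with two incompatible instructions.

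Finally, the SAP does not say outright that equal weights are intended, and the documents do not show whether the 50% wording or the 4-of-8 example is the intended rule. Equal weighting is inferred from the division by 6 and the stated range; the threshold is for the sponsor to decide.

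**Conclusion.** The concern holds. As written, the formula gives domain ranges of 3-21, 5-35 and 8-56 and a total of 4.83-33.83, against a stated 1-7 for all of them. Absolute domain scores and changes, with their confidence limits, are inflated by a factor of 3, 5 or 8. The total weights domains from 10.3% to 27.6% instead of 16.7% each. The missing-data rule is inconsistent for the 8-item domain.

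This rests on the item scale, item allocation and formulas in SAP 9.4.9.2, and on the formula being programmed literally; no outside scoring manual is needed. The analysis affected is exploratory, but the scores feed both clinical study reports planned in SAP 7.14. SAP 4.2 records that the FACIT-Fatigue and PedsQL scoring text was corrected in this version, so putting the CLDQ right is the same kind of change. It needs settling before the scores are derived for reporting.

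**What to change.** In SAP 9.4.9.2:

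1. Replace the domain formula with: domain score = sum of answered item scores divided by the number of items answered in that domain.
2. Keep the total as the sum of the six domain scores divided by 6, and say that it is the unweighted mean of the six domains. Both then run 1-7, as the section already states.
3. State one missing-data threshold. If more than half is meant, the minimums are 2 of 3, 3 of 5 and 5 of 8. If 4 of 8 is meant, the wording should say at least half; the minimums for the 3- and 5-item domains do not change.

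The cost is a few lines of SAP text and the matching derivation code, plus a check that every derived domain and total lies within 1-7. No new data are needed. If any CLDQ tables have already been produced with the written formula, rerun them.
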